**8.0****Efficacy Analyses****8.1****General Considerations**

All summary statistics for the efficacy and usability analysis will be conducted in the ITT Population. No statistical tests will be performed.

All efficacy endpoints will be summarized up to Week 28 during this analysis.

Categorical variables will be summarized by frequencies, percentages, and the 95% confidence intervals (CIs). Continuous variables will be summarized by least square mean, standard error, and the 95% CIs.

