**8.2****Handling of Missing Data**

Missing data will be imputed using the following methods for the efficacy analyses:

- Non-Responder Imputation (NRI): The NRI analysis will categorize any subject who does not have evaluation during a specific visit window as a non-responder for that visit. The exceptions are: (1) if the subject is a responder both before and after a specific visit window in the particular period, then the subject will be categorized as a responder for the visit; (2) when the subject missed a visit due to COVID-19 pandemic, the missing assessment from that visit will be imputed using Multiple Imputation (MI) to determine the corresponding response status. In present study, only Week 28 or later visits may be affected by the COVID-19 pandemic. The NRI will be the primary missing data imputation approach in the analyses of categorical variables.
- Modified-NRI: Patients who discontinue study drug due to lack of efficacy or due to AE of worsening of psoriasis and do not have Week 16 measurements will be counted as non-responders. Other patients will be summarized using as-observed data. The modified-NRI analysis will be the sensitivity approach to handle missing data in the analysis of key efficacy endpoints specified in Section 3.1.
- As-observed: The as-observed analysis will include all available assessments on a scheduled visit. No missing assessments will be imputed. The as-observed analysis will be the sensitivity approach to handle missing data in the analysis of the key efficacy endpoints specified in Section 3.1.
- Mixed-effect Model Repeat Measurement (MMRM): The repeated measures analysis will be conducted using a mixed model including baseline value and observed measurements at all post-baseline visits, using all available data even if a subject has missing data at some post-baseline visits. The mixed model includes visit as the covariate. An unstructured variance covariance matrix will be used. Parameter estimation is based on the assumption of data being missing at random and using the method of restrictive maximum likelihood (REML). MMRM will be the primary approach in the analysis of continuous variables.

The key usability endpoints will be summarized by as-observed cases.

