**8.5                   Additional Efficacy Analyses**

All key efficacy endpoints will be analyzed at all other visits collected. Additional variables to be provided will include the proportion of subjects achieving PASI 50, as well as change and percent change from baseline in PASI, at each visit collected.

Non-Responder Imputation (NRI) will be used for categorical endpoints to handle missing data. Mixed-effect Model Repeat Measurements (MMRM) will be used for continuous endpoints.

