#### **9.4 Analysis of Vital Signs**

Vital sign measurements of systolic and diastolic blood pressure will be summarized.

Mean change from baseline to each applicable post-baseline visit will be summarized for each vital sign variable, with the number of observations, baseline mean, and visit mean. The change from baseline mean, standard error, and 95% confidence interval will be presented for the mean change from baseline.

Vital sign variables will be evaluated based on potentially clinically important (PCI) criteria ([Appendix C](#)). For each vital sign PCI criterion, the number and percentage of subjects who have a vital sign value meeting the criteria will be summarized. Listings will be provided to summarize subject-level vital sign data for subjects meeting PCI criteria.

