## 13.0 Version History

**Table 1. SAP Version History Summary**

Version	Date	Summary
1.0	28 Nov 2018	Original version
2.0	02 Jan 2019	Added more statistical analysis details to the document. Deleted the wording of "blinded efficacy assessor" to be consistent with the protocol admin change 1.
3.0	19 Jul 2019	Added more statistical analysis details to the document.
4.0	17 Apr 2020	Clarified weight and BMI categories in demographics. Clarified items to be summarized for disposition to align with the new standard table. Removed baseline BSA from MMRM model in efficacy analysis, as most BSA information is covered by the corresponding components in baseline PASI. Updated the definition of concomitant medication to align with the most updated risankizumab PSSAP. Clarified shift tables, PCI, and ASI definitions for safety analysis, to align with the most updated risankizumab PSSAP. Corrected the dates in version history. Added the AE summary of any injection site reactions, according to FDA suggestion. Added details about how to handle missing data due to COVID-19 in the NRI analysis. Added modified-NRI and as-observed sensitivity analyses for the key efficacy endpoints. Added sPGA clear at Week 16 to key efficacy endpoints.
5.0	22 Apr 2020	Corrected a typo at Section 8.3.1 that there are 4 critical steps in the Instructions for Use (IFU) of achieving an observer rating of successful subject self-administration.

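### If baseline PASI is a covariate in the single-arm MMRM, the 95% CI for mean absolute change in PASI leaves out baseline sampling variance and is too narrow for the population mean change

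*SAP*

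**What the plan says.** SAP section 8.5 lists two continuous efficacy variables, "as well as change and percent change from baseline in PASI, at each visit collected", and assigns their analysis: "Mixed-effect Model Repeat Measurements (MMRM) will be used for continuous endpoints".

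Section 8.2 describes the model: "The repeated measures analysis will be conducted using a mixed model including baseline value and observed measurements at all post-baseline visits". It adds "The mixed model includes visit as the covariate" and "An unstructured variance covariance matrix will be used", with REML estimation under missing at random. Section 8.1 fixes the output: "Continuous variables will be summarized by least square mean, standard error, and the 95% CIs".

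The entry for version 4.0 in the version history (section 13.0) helps to interpret the current text: "Removed baseline BSA from MMRM model in efficacy analysis, as most BSA information is covered by the corresponding components in baseline PASI".

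For vital signs, section 9.4 uses an ordinary summary: "The change from baseline mean, standard error, and 95% confidence interval will be presented for the mean change from baseline". Section 9.3 does the same for laboratory data.

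The SAP does not say whether the interval for PASI change refers to the population mean change or to the mean change at the observed mean baseline.

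**The concern.** In a randomised trial, baseline adjustment sharpens the contrast between arms, and the baseline variance common to both arms is of no interest. This study has one arm and no contrast. With complete data, the least squares mean evaluated at the sample-mean baseline equals the raw mean change, so adjustment leaves the estimate where it was. What changes is the standard error. The model treats the observed baselines as fixed and drops the variability that comes from having sampled these subjects rather than others.

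For a drug that clears most disease, absolute change is close to minus the baseline value. Baseline variance is then a large share of the variance of change, and that is the share the model SE removes. A reader who sees an unqualified 95% CI for mean change will take it as a statement about the patient population and will think the mean is known more precisely than it is. The same report would also contain mean-change CIs for laboratory and vital-sign data that do keep this variance, so one label would carry two meanings.

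**Working it through.** **Reproducing the SAP's own precision figures.** The SAP states no precision for mean change in PASI. The figures it does give, in section 2.4 for n = 100, follow from 1.96·√(p(1−p)/n):

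- p = 0.90: 1.96·√(0.09/100) = 5.88 points (stated 5.9)
- p = 0.74: 1.96·√(0.1924/100) = 8.60 points (stated 8.6)
- p = 0.85: 1.96·√(0.1275/100) = 7.00 points (stated 7.0)

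All three reproduce.

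**Inputs for the check.** From the SAP: n = 100, a single arm, and a 95% level. Assumed, because the SAP gives none of them: baseline SD s_B, residual SD s_e, and the slope b of post-baseline PASI on baseline PASI.

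As a plausibility check on s_e, a 74% PASI 90 rate (section 2.4), an assumed mean baseline of 20, and exponential or lognormal residual fractions imply a Week 16 residual SD of about 1.5 to 4.6.

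**Formulas.** Write post-baseline PASI as Y = a + b·B + e. Then, for the mean of Y − B:

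- model SE, with baseline as a fixed covariate: s_e/√n
- sampling SE of the same estimate: √(s_e² + (1−b)²·s_B²)/√n
- ratio r = s_e/√(s_e² + (1−b)²·s_B²)
- coverage of the nominal 95% CI for the population mean change: 2Φ(1.96·r) − 1

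**Worked case: s_B = 8, s_e = 3, b = 0.05.** (0.95·8)² = 57.76, and 57.76 + 9 = 66.76, whose root is 8.17. The half-widths are 1.96·3/10 = 0.59 and 1.96·8.17/10 = 1.60 PASI points. So r = 0.37 and coverage is 2Φ(0.72) − 1 = 53%.

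**Range at Week 16 and later, n = 100**

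| s_B | s_e | b | Model half-width | Unconditional half-width | Coverage |
|---|---|---|---|---|---|
| 10 | 3 | 0.05 | 0.59 | 1.95 | 44% |
| 8 | 3 | 0.05 | 0.59 | 1.60 | 53% |
| 8 | 4 | 0.1 | 0.78 | 1.61 | 66% |
| 6 | 3 | 0.05 | 0.59 | 1.26 | 64% |
| 4 | 3 | 0.05 | 0.59 | 0.95 | 78% |
| 4 | 4 | 0.1 | 0.78 | 1.06 | 86% |
| 4 | 8 | 0.05 | 1.57 | 1.74 | 92% |

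The last row is deliberately unfavourable to the point. In the other direction, s_e = 1.5 with b = 0.05 gives 24% (s_B = 10) to 53% (s_B = 4).

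**Simulation.** A repeated-measures model with baseline and visit as fixed effects and an unstructured covariance was fitted to complete data at three post-baseline visits, with n = 100 and 3,000 runs per setting.

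- Week 16, s_e = 3: coverage 79%, 66%, 55% and 46% for s_B = 4, 6, 8 and 10, in line with the formula.
- Week 4, assumed slope 0.4 and s_e of 4 to 6: 84% to 93%.
- Unadjusted mean-change CI: 93% to 95% at every visit and setting.
- Percent change, simulated with no dependence on baseline: 93.3% adjusted against 93.2% unadjusted in one setting, and 94.3% against 94.2% in the other. There is no material narrowing.

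**The case against.** **The SAP may not intend baseline as a covariate.** Section 8.2 gives that name to visit alone. Its sentence on baseline and post-baseline values can be read as listing the data, with visit as the only fixed effect. That would be the model recommended below, and the problem would disappear. This stands as a real ambiguity. The covariate reading is still the more natural one: baseline value is named apart from the post-baseline measurements, and dropping BSA because baseline PASI covers it makes sense only if baseline PASI is a term in the model. The version history supports that reading; it does not prove it.

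**The interval is valid for its own target.** It is a correct CI for mean change at the observed mean baseline. That is true, and the SAP sets no other target. But it does not state this one either, and an unqualified CI for a mean change is ordinarily read as a population interval.

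**The size is assumed.** A reader might infer that the intervals are certain to be far too narrow. The SAP cannot support that: it gives no SDs and no slope, and the shortfall runs from slight to severe across the values tried.

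**Little depends on it.** A reader might also infer that the study's efficacy results are compromised. They are not. Absolute change in PASI is an additional variable, the key efficacy endpoints are proportions, the usability endpoints do not use this model, and sections 8.1 and 12.0 exclude statistical tests. The SAP plans no comparison of mean changes with other studies.

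**Conclusion.** The point holds, within limits. If baseline PASI is a fixed covariate, the planned 95% CI for mean absolute change in PASI omits baseline sampling variance and is too narrow for the population mean change. Under the main assumptions (n = 100, baseline SD 4 to 10, residual SD 3 to 4, slope 0.05 to 0.1, complete data), its coverage at Week 16 and later is about 44% to 86%. A large residual SD with a small baseline SD brings it close to nominal.

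The direction follows from the model. The size does not follow from anything the SAP states. The effect is confined to the error bars of one additional descriptive variable. It deserves correction because no sensitivity analysis is planned for continuous variables, so this model is the only source of uncertainty for that result.

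**What to change.** State in section 8.2 that, for absolute change in PASI, the repeated-measures model takes PASI at all visits including baseline as the response, with visit as the only fixed effect and an unstructured covariance. Report visit-minus-baseline contrasts with their SE and 95% CI. This keeps the missing-at-random handling and all subjects, and it settles baseline's role in the model.

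A simpler alternative is to fit the model for change without the baseline covariate.

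The cost is one sentence and minor programming. The reported intervals for mean change will be wider: under the worked assumptions, 1.60 rather than 0.59 points on either side.

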## **8.3 Efficacy and Usability Analysis**

### **8.3.1 Key Usability Analysis**

The following key usability endpoints will be evaluated:

- Proportion of subjects with an Observer rating of successful subject self-administration, defined as any subjects who successfully completed the sequence of 4 critical steps in the Instructions for Use (IFU) without errors to administer study drug via the AI at Week 0 and Week 28
- Proportion of subjects who had no potential hazards as measured by an Observer on the possible use-related hazards checklist for self-administration with AI at Week 0 and Week 28
- Subject rating of acceptability by the Self-Injection Assessment Questionnaire (SIAQ) at each visit collected.

### **8.3.2 Handling of Missing Data for the Key Usability Analysis**

The key usability endpoints will be summarized by as-observed cases.

## **8.4 Key Efficacy Analysis**

The following key efficacy endpoints will be evaluated:

- Proportion of subjects achieving PASI 90 at Week 16
- Proportion of subjects achieving sPGA clear or almost clear at Week 16
- Proportion of subjects achieving PASI 100 at Week 16
- Proportion of subjects achieving PASI 75 at Week 16
- Proportion of subjects achieving sPGA of clear at Week 16.

Key efficacy endpoints at Week 16 will be analyzed using NRI method to handle missing data. Modified-NRI analysis and as-observed analysis will also be performed to handle missing data as sensitivity analyses.

**8.4.1                   Supportive Secondary Efficacy Analyses**

There are no additional supportive secondary efficacy analyses planned other than those described above.

**8.5                   Additional Efficacy Analyses**

All key efficacy endpoints will be analyzed at all other visits collected. Additional variables to be provided will include the proportion of subjects achieving PASI 50, as well as change and percent change from baseline in PASI, at each visit collected.

Non-Responder Imputation (NRI) will be used for categorical endpoints to handle missing data. Mixed-effect Model Repeat Measurements (MMRM) will be used for continuous endpoints.

**8.6                   Efficacy Subgroup Analyses**

No efficacy subgroup analyses are planned.

**9.0                   Safety Analyses****9.1                   General Considerations**

Safety data will be summarized for the Safety Analysis Population. Safety analyses will include adverse events, laboratory, and vital sign measurements.

Missing safety data will not be imputed.

**9.2                   Adverse Events**

Adverse events (AEs) will be summarized and presented using primary MedDRA System Organ Classes (SOCs) and preferred terms (PTs) according to the version of the MedDRA coding dictionary used for the study at the time of database lock. The actual version of the MedDRA coding dictionary used will be noted in the AE tables and in the clinical study report. When summarizing the number and percentages of subjects, subjects with multiple occurrences of the same adverse event will be counted once, and only the

maximum severity level will be presented in the severity summaries, and the worst/highest relationship level in the relationship summaries.

### **9.2.1 Treatment-Emergent Adverse Events**

Treatment-emergent adverse events (TEAEs) are defined as any event newly developed on or after the first dosing of study drug to 20 weeks (140) days after the last dose of study drug.

### **9.2.2 Adverse Event Overview**

An overview of TEAEs will be presented consisting of the number and percentage of subjects experiencing at least one event for each of the following AE categories:

- Any treatment-emergent AE
- Any treatment-emergent AE related to study drug according to the investigator
- Any severe treatment-emergent AE
- Any serious treatment-emergent AE
- Any treatment-emergent AE leading to discontinuation of study drug
- Any adjudicated MACE
- Any infection
- Any serious infection
- Any tuberculosis
- Any malignant tumor
- Any malignant tumor excluding NMSC
- Any serious hypersensitivity
- Any treatment-emergent AE leading to death

All deaths will also be summarized:

- Deaths occurring  $\leq$  140 days after last dose of study drug
- Deaths occurring  $>$  140 days after last dose of study drug.

**9.2.3****Treatment-Emergent Adverse Events by SOC and/or PT**

Treatment-emergent adverse events will be summarized by SOC and PT; by maximum relationship to study drug as assessed by the investigator (e.g., reasonable possibility or no reasonable possibility) and by SOC and PT; by maximum severity and by SOC and PT; and by SOC and PT listing associated subject number. When summarizing the number and percentages of subjects, subjects with multiple occurrences of the same adverse event will be counted once, and only the maximum severity level will be presented in the severity summaries, and the worst/highest relationship level in the relationship summaries.

In addition, treatment-emergent adverse events will be summarized by PT and sorted by decreasing frequency.

**9.2.4****Treatment-Emergent Adverse Events per Patient-Years of Exposure**

Exposure-adjusted AEs per 100 patient-years will be provided, where AEs per 100 patient-years of exposure are defined as the number of AEs divided by the total exposure in 100 patient-years.

Note that one event per preferred term per day per subject will be counted in the calculation of the number of AEs (i.e., a preferred term will not be counted twice on the same day for the same subject). See the calculation method below.

$$100 \times \frac{\text{Number of TEAEs}}{\text{Total Patient Years}},$$

where total patient years is defined as the sum of the study drug exposure (defined as date of last dose – date of first dose + 140 days (5 half-lives)) of all subjects normalized by 365.25, and rounded to one decimal place.

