## 2.2 Study Design Overview

This is a Phase 3 multicenter, single-arm, open-label study that will evaluate usability of the risankizumab-AI combination product. In addition, efficacy will be evaluated by an efficacy assessor. The study includes a 30-day screening period with study visits at Week 0, 4, 16, 28, and 40 with a subsequent follow-up telephone call at approximately 20 weeks after the last dose of study drug (Week 48). Study drug dosing will consist of four self-administered doses given subcutaneously on Weeks 0, 4, 16, and 28. Dosing on Week 4 and Week 16 will be self-administered at home. Efficacy assessments will be performed at each study visit (Weeks 0, 4, 16, 28, and 40).

The schematic of the study is shown in [Figure 1](#).

**Figure 1.** Study Schematic

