## **5.0                   Subject Disposition**

The total number of subjects who were treated, completed, and discontinued will be summarized.

A summary of subject accountability will be provided where the number of subjects in each of the following categories will be summarized:

- Subjects who received at least one study drug;
- Subjects who completed study;
- Subjects who discontinued study drug (all reasons and primary reason);
- Subjects who discontinued study (all reasons and primary reason)

For end of study participation, the number and percentage of subjects who completed this study (or did not with associated reasons) will be summarized overall.

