**11.2                   Interim Analysis**

An interim analysis will occur after all ongoing subjects complete the Week 28 Visit. All efficacy variables up to Week 28, as well as all observed safety and usability variables, will be summarized during this analysis.

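### Exposure for the per-100-patient-year TEAE rates adds 140 days after the last dose for everyone, with no cap at death, study exit or data cut-off, so the rates are too low wherever follow-up ends sooner

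*SAP*

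**What the plan says.** Section 9.2.4 defines the rate as 100 times the number of TEAEs over total patient-years. Patient-years are the "study drug exposure (defined as date of last dose – date of first dose + 140 days (5 half-lives)) of all subjects", divided by 365.25. The SAP gives no alternative end date for a subject who dies, leaves the study or is still in follow-up when the data are cut.

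Four other places bear on this:

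- **Numerator, Section 9.2.1:** a TEAE is "any event newly developed on or after the first dosing of study drug to 20 weeks (140) days after the last dose of study drug".
- **Missing data, Section 9.1:** "Missing safety data will not be imputed".
- **Schedule, Section 2.2:** doses fall at Weeks 0, 4, 16 and 28, and the plan ends with a "follow-up telephone call at approximately 20 weeks after the last dose of study drug (Week 48").
- **Interim, Section 11.2:** "An interim analysis will occur after all ongoing subjects complete the Week 28 Visit". Efficacy up to that visit, "as well as all observed safety and usability variables, will be summarized during this analysis". The exposure-adjusted table is neither named nor excluded, and no separate exposure rule is given.

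The SAP foresees follow-up that ends early. Section 9.2.2 tabulates deaths within 140 days of the last dose, and Section 5.0 tabulates subjects who leave the study.

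**The concern.** The denominator of an event rate should hold the time in which an event could have been recorded. Here the numerator holds only recorded events, while the denominator holds a planned follow-up that may not have happened. The two agree only for subjects followed for about 20 weeks after their last dose.

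They can part in two settings. At any analysis, a subject who dies or leaves the study within 140 days of the last dose is credited with the rest of the 140 days. At the Week 28 interim, most subjects may be only days or weeks past their last dose, so the formula can credit dates that have not yet occurred. Stopping study drug alone causes no error if the subject is still followed.

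The added person-time always pushes the rate down, which is the unwelcome direction for a safety summary. Interim and final rates from the same study would also rest on different bases: partly projected time in one and nearly all observed time in the other.

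**Working it through.** **Inputs from the SAP.** 100 subjects (2.4); last planned dose at Week 28, day 28 × 7 = 196 (2.2); tail of 140 days (9.2.4); TEAE window to 140 days after the last dose (9.2.1); planned end of follow-up at Week 48 (2.2).

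**Assumptions, not in the SAP.** All subjects dosed through Week 28 for the interim calculation; uniform accrual over E days; a lag of L days from the last subject's Week 28 visit to the data cut-off; chosen numbers of early leavers for the final analysis.

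**Step 1: the SAP's own figures.** 20 weeks × 7 = 140 days, and (196 + 140)/7 = 48 weeks. For a subject who completes as planned, the tail, the TEAE window and the follow-up call coincide. Credited time is 196 + 140 = 336 days each, or 100 × 336/365.25 = 92.0 patient-years (PY).

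**Step 2: size of the error.** Reported rate = events/credited PY. Rate over observed time = events/observed PY. So the understatement is 1 − observed PY/credited PY.

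**Step 3: interim.** With uniform accrual, the time from a subject's Week 28 visit to the cut-off is L + U, with U uniform on 0 to E. Mean observed days are 196 + mean of min(140, L + U). When L + E ≥ 140 this equals 196 + 140 − (140 − L)²/(2E).

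Example, L = 0 and E = 140: 336 − 19,600/280 = 266.0 days; 100 × 266.0/365.25 = 72.8 PY; understatement 1 − 266.0/336 = 20.8%.

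Mean observed days per subject, with the understatement in brackets:

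| Lag L | E = 140 d | E = 280 d | E = 365 d |
|---|---|---|---|
| 0 d | 266.0 (20.8%) | 301.0 (10.4%) | 309.2 (8.0%) |
| 30 d | 292.8 (12.9%) | 314.4 (6.4%) | 319.4 (4.9%) |
| 60 d | 313.1 (6.8%) | 324.6 (3.4%) | 327.2 (2.6%) |
| 90 d | 327.1 (2.7%) | 331.5 (1.3%) | 332.6 (1.0%) |

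Against 92.0 PY credited, observed PY are 72.8 / 82.4 / 84.6 with no lag and 80.2 / 86.1 / 87.5 with a 30-day lag. The upper bound, with everyone enrolled on one day and no lag, is 196 of 336 days, or 41.7%. It is theoretical only.

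**Step 4: final analysis.** With complete follow-up, observed and credited time are equal and the error is 0%. Suppose instead that k of 100 subjects leave 28 days after a single dose. Credited days are (100 − k) × 336 + k × 140, and observed days are (100 − k) × 336 + k × 28.

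| k | Credited PY | Observed PY | Understatement |
|---|---|---|---|
| 2 | 90.9 | 90.3 | 0.7% |
| 5 | 89.3 | 87.8 | 1.7% |
| 10 | 86.6 | 83.6 | 3.5% |

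**The case against.** The best defence is that the definition is coherent as planned. The 140-day tail, the TEAE window and the Week 48 call all match, and the tail is described as drug exposure over five half-lives, not as follow-up. That coherence is real for completers at the final analysis. It does not rescue the formula elsewhere, because Section 9.2.4 uses this quantity as time at risk for an event rate, and that time ends when observation ends.

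Several limits do stand:

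- The interim error depends on the table being produced then, and on accrual and lag, which the SAP does not give. The results run from 20.8% to 1.0% across the cases shown.
- The protocol is not at hand, and adverse events may still be collected after a subject leaves the study. If so, the error for early leavers is smaller. It remains for deaths and for subjects whose contact is lost.
- The rate over observed time is the benchmark used here. If events cluster early in treatment, a capped interim rate would exceed the rate over the full 336 days. A cap removes the unobserved time but does not make interim and final rates cover the same period.
- There is one arm and no statistical test. Counts, percentages, listings and death summaries do not use this denominator.

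**Conclusion.** The concern holds. As written, Section 9.2.4 gives a rate biased downward for any subject whose observation ends within 140 days of the last dose, and no other section corrects it. At the final analysis the effect is nil with complete follow-up and at most a few percent under the assumed numbers of early leavers. At the Week 28 interim it could be material: about 8% to 21% with no lag, about 5% to 13% with a 30-day lag, and 1% to 3% with a 90-day lag, for uniform accrual over 365 down to 140 days. Those interim figures apply only if the per-100-patient-year table is run then. The point should be fixed, but it affects one set of descriptive rates and no inference.

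**What to change.** In Section 9.2.4, define each subject's exposure as the earliest of (last dose + 140 days, death, last contact or study discontinuation, analysis data cut-off) minus the first dose date, keeping the section's existing day count. Count TEAEs over that same interval, at both the interim and the final analysis. In Section 11.2, state whether the per-100-patient-year table is part of the interim.

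This costs one sentence, one clause and a small programming change. Nothing changes for subjects followed as planned to Week 48. Where follow-up is shorter, the reported rates will be somewhat higher.
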